1	Rheumatic disease	Medical claim with an ICD-10 code in the inpatient or non-IP setting for rheumatic disease (dichotomous)	180 days prior to index date to index
1	Peptic ulcer disease	Medical claim with an ICD-10 code in the inpatient or non-IP setting for peptic ulcer disease (dichotomous)	180 days prior to index date to index
1	Liver disease	Medical claim with an ICD-10 code in the inpatient or non-IP setting for liver disease (dichotomous)	180 days prior to index date to index
1	Diabetes	Medical claim with an ICD-10 code in the inpatient or non-IP setting for diabetes (dichotomous)	180 days prior to index date to index
1	Renal disease	Medical claim with an ICD-10 code in the inpatient or non-IP setting for renal disease (dichotomous)	180 days prior to index date to index date
1	Hemiplegia or paraplegia	Medical claim with an ICD-10 code in the inpatient or non-IP setting for hemiplegia or paraplegia (dichotomous)	180 days prior to index date
1	Human immunodeficienc y virus	Medical claim with an ICD-10 code in the inpatient or non-IP setting for human immunodeficiency virus (dichotomous)	180 days prior to index date to index date

Objective	Variable	Definition	Assessment Period(s)
1	Metastatic solid tumor	Medical claim with an ICD-10 code in the inpatient or non-IP setting for metastatic solid tumor (dichotomous)	180 days prior to index date to index date

Table 3 includes definitions and assessment periods for all study variables being used as outcomes. The full code list can be found in ANNEX 2. ADDITIONAL INFORMATION. If applicable, the frequency and percentage of patients with missing data for each variable will be described.

Table 3. Key Variables of Interest

Objective	Variable	Definition	Assessment Period(s)
Treatment ex	posure		
2	Use of supportive MM medications	Medical or pharmacy claim with evidence of an NDC, HCPCS, generic name or CPT code for the following medications (dichotomous):	Index date to the end of follow-up Index date Step-Up Dosing Period Maintenance Periods
2	Reported vial size	Reported vial size in the following categories (categorical): • Unknown vial – inpatient dose • 44mg/1.1mL • 76mg/1.9mL • Missing dose/unknown dose For the cohort of teclistamab patients the reported vial size (categorical): • Unknown vial – inpatient dose • 30mg/3mL • 153mg/7mL • Missing dose/unknown dose	Index date to the end of follow-up Index date Step-Up Dosing Period Maintenance Periods

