Exploratory Obj 1	Other infectious hepatitis ²	Medical claim with an ICD-10 code in the inpatient, non-IP or pharmacy setting for infectious hepatitis (other than hepatitis B or C) (dichotomous)	Index date to end of follow-up, where follow-up will be based on last dose of elranatamab or teclistamab (e.g., 14 days after last recorded dose or 90 days after last recorded dose).
Exploratory Obj 1	Helicobacter pylori ²	Medical claim with an ICD-10 code in the inpatient, non-IP or pharmacy setting for helicobacter pylori (dichotomous)	Index date to end of follow-up, where follow-up will be based on last dose of elranatamab or teclistamab (e.g., 14 days after last recorded dose or 90 days after last recorded dose).

Exploratory Obj 1	Candida esophagitis ²	Medical claim with an ICD-10 code in the inpatient, non-IP or pharmacy setting for candida esophagitis (dichotomous)	Index date to end of follow-up, where follow-up will be based on last dose of elranatamab or teclistamab (e.g., 14 days after last recorded dose or 90 days after last recorded dose).				
Exploratory Obj 1	Urinary tract infection ²	Medical claim with an ICD-10 code in the inpatient, non-IP or pharmacy setting for a urinary tract infection (dichotomous)	Index date to end of follow-up, where follow-up will be based on last dose of elranatamab or teclistamab (e.g., 14 days after last recorded dose or 90 days after last recorded dose).				
Exploratory Obj 1	Time to infection onset	Time in days from index date to first infection for the following infections:	Index date until censor				
Effectiveness	Effectiveness						
Exploratory Obj 2	os	Time (in months) from index date until date of death (continuous)	Index date until censor				
Exploratory Obj 2	TTNT/D	Time (in months) from index date until the date of the next treatment (CAR-T, BsABs, bendamustine or belantamab) or death (continuous)	Index date until censor				

- 1. Variable will be measured as incident and prevalent. Incident cases have 30-day washout period applied
- 2. Variable will be measured as incident and prevalent. Incident cases have 60-day washout period applied
- 3. Variable will be measured as incident and prevalent. Incident cases have 14-day washout period applied

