9.5. Study Size

As of August 2024, the dataset included 133 patients with a claim for elranatamab. To further assess whether sufficient sample size is available to proceed with the study, power analysis will be completed to assess estimates of precision for a one sample means considering either the elranatamab or teclistamab samples.

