9.8. Quality Control

Clarify Health will code measures for cohort identification, outcomes, and other variables of interest based on codes and algorithms described in this protocol. This protocol will be strictly followed when conducting the analysis of this study. All cohorts developed, statistical analyses implemented, and tables completed will undergo quality control review by at least one additional analyst or scientist under the supervision of the Study Lead. The Study Lead will review all results tables and other final deliverables to confirm accuracy, logical flow, and appropriate format.

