	Clinical, Adverse event		E13.41, G57.70, G57.71, G57.72, G57.73, G59, G57.80, G57.81, G57.82, G57.83, G58.8, G58.9, G64., G61.0, M05.50, M05.511, M05.512, M05.519, M05.521, M05.522, M05.529, M05.531, M05.532, M05.539, M05.541, M05.542, M05.549, M05.551, M05.552, M05.559, M05.551, M05.552, M05.559, M05.571, M05.572, M05.579, M05.59, E08.40, E08.42, E09.40, E09.42, E10.40, E10.42, E11.40, E11.42, E13.40, E13.42, G13.0, G13.1, A36.83, A52.15, G63, M34.83, G62.1, G61.1, G62.0, G62.2, G62.82, G61.81, G62.81, G61.89, G62.89, G61.9, G62.9, H46.3, M54.10, M54.18, M79.2, R20.0, R20.1, R20.2, R20.3, R20.8, R20.9
Any infection	Baseline characteristic - Clinical	Claims data	An ICD-10 Diagnosis Code for any of the following types of infections. See the rows below for codes for each infection type. COVID-19, Adenoviral pneumonia, Cytomegaloviral pneumonitis, Other Pneumonia, Upper respiratory tract infection, Sepsis, Cytomegaloviral infection, Pneumocystis jiroveci pneumonia (PJP), Hepatitis C, Hepatitis B, Other infectious hepatitis, Helicobacter pylori, Candida esophagitis, Urinary tract infection
Use of intravenous anti- infective	Baseline characteristic - Clinical	Claims data	See "Antivirals" and "Antibiotics" above
Neutropenia	Baseline characteristic - Clinical, Adverse event	Claims data	ICD-10 Diagnosis: D70x
Hypercalcemia	Baseline characteristic - Clinical	Claims data	ICD-10 Diagnosis: E83.52
Hypoxia	Baseline characteristic - Clinical, Adverse event	Claims data	ICD-10 Diagnosis: J96.20, J96.11, J96.90, J96.01, J96.00, J96.10, J96.21, J96.91, I27.23, R09.02
Hepatotoxicity	Baseline characteristic - Clinical, Adverse event	Claims data	ICD-10 Diagnosis: K71.x
Renal failure	Baseline characteristic -	Claims data	ICD-10 Diagnosis: N17x, N18x, N19x, R34x, T82.4, Z49.02, Z99.2

	Clinical, Adverse event		
Amyloidosis	Baseline characteristic - Clinical	Claims data	ICD-10 Diagnosis: E85.4x, E85.8x, E85.9x
Hypertension	Baseline characteristic - Clinical	Claims data	ICD-10 Diagnosis: I10x-I15x, I16x
Extramedullary disease	Baseline characteristic - Clinical	Claims data	ICD-10 Diagnosis: C90.2x
CCI score	Baseline characteristic - Clinical	Claims data	See components below
Myocardial infarction	Baseline characteristic - Clinical	Claims data	ICD-10 Diagnosis: I21.x, I22.x, I25.2
Congestive heart failure	Baseline characteristic - Clinical	Claims data	ICD-10 Diagnosis: I11.0, I13.0, I13.2, I25.5, I42.0, I42.5, I42.6, I42.7, I42.8, I42.9, I43.x, I50.x, P29.0

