Cytomegaloviral infection	Adverse event - infection	Claims data	ICD-10 Diagnosis: B25.0, B25.1, B25.2, B25.8, B25.9, B27.0, B27.1, B27.2, B27.9
РЈР	Adverse event - infection	Claims data	ICD-10 Diagnosis: B59
Hepatitis C	Adverse event - infection	Claims data	ICD-10 Diagnosis: B17.1x, B18.2, B19.2x
Hepatitis B	Adverse event - infection	Claims data	ICD-10 Diagnosis: B16.x, B17.0, B18.0, B18.1, B19.1x
Other infectious hepatitis	Adverse event - infection	Claims data	ICD-10 Diagnosis: B17.2, B17.8, B17.9, B18.8, B18.9, B19.0, B19.9
Helicobacter pylori	Adverse event - infection	Claims data	ICD-10 Diagnosis: B96.81
Candida esophagitis	Adverse event - infection	Claims data	ICD-10 Diagnosis: B37.81
Urinary tract infection	Adverse event - infection	Claims data	ICD-10 Diagnosis: N39.0

Document Approval Record

Document Name:

C1071044_NON-INTERVENTIONAL STUDY PROTOCOL_V2_06AU G2025

Document Title:

C1071044_NON-INTERVENTIONAL STUDY PROTOCOL_V2_06AU G2025

Signed By:	Date(GMT)	Signing Capacity
Redacted	02-Sep-2025 15:50:58	Final Approval
Redacted	03-Sep-2025 15:07:21	Manager Approval

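### Annex 2 codes urinary tract infection by N39.0 alone, so patients whose only coded urinary infection is site-specific (acute pyelonephritis, acute cystitis) are missed.

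*Protocol*

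**What the plan says.** Protocol section 9.3, Table 3, defines the outcome under Exploratory Objective 1 as: "Medical claim with an ICD-10 code in the inpatient, non-IP or pharmacy setting for a urinary tract infection (dichotomous". No site or severity restriction is attached. For the codes, section 9.3 refers the reader onward: "The full code list can be found in ANNEX 2. ADDITIONAL INFORMATION".

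The urinary tract infection row of Annex 2 reads, in full, "ICD-10 Diagnosis: N39.0". There is no wildcard and no second code.

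The same row is used in two further places. For the baseline any-infection variable, Annex 2 gives no separate list but says: "See the rows below for codes for each infection type". Footnote 2 of Table 3, which applies to this outcome, adds for incidence: "Incident cases have 60-day washout period applied".

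Section 9.8 says that measures are coded from the codes and algorithms in the protocol, and that "This protocol will be strictly followed when conducting the analysis of this study".

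**The concern.** The name of the outcome is broader than its code. A urinary infection whose site the clinician recorded is still a urinary tract infection, but it is normally coded to its site, and the Annex 2 row does not accept those codes. The loss falls on patients with site-coded infection, and that group includes kidney infection.

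Infections are among the adverse events the abstract names for reporting. The row also helps to define a baseline characteristic under primary Objective 1 and the washout for incident cases, and it applies to the teclistamab cohort as well. A reader of the final report would take the UTI line at face value, since nothing in the protocol says that it covers unspecified-site infection only.

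**Working it through.** The protocol gives no figure for this outcome, so there is nothing to reproduce. The check is a comparison of definition and code list, followed by an illustration with assumed inputs.

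**1. Definition against codes.**
- Table 3: urinary tract infection, any site.
- Annex 2: N39.0 only.
- Meaning of the codes: the protocol prints no descriptors. In the ICD-10 nomenclature it uses, N39.0 is urinary tract infection with site not specified, N10 is acute pyelonephritis and N30.0x is acute cystitis.

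**2. Are the missing codes elsewhere in Annex 2?** No row holds N10, N12 or any N30 code. The remaining kidney codes serve renal failure and renal disease (N17x, N18x, N19x, N03.x, N05.x and the like). Site-coded urinary infections are therefore not picked up as UTI through another row.

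**3. Who is lost.** The variable is dichotomous per patient, and section 9.7.6 assesses it from index to 14 or 90 days after the last administration. A patient is missed only if at least one urinary infection is coded to its site and no claim in that window carries N39.0.

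**4. Prevalence.** Let p be the true prevalence and m the share of affected patients with no N39.0 claim in the window. Then

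reported prevalence = p × (1 − m).

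Neither p nor m is in the documents. The assumed ranges are p = 10% to 30% and m = 5% to 30%.

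| True p | m = 5% | m = 10% | m = 20% | m = 30% |
|---|---|---|---|---|
| 10% | 9.5% | 9.0% | 8.0% | 7.0% |
| 20% | 19.0% | 18.0% | 16.0% | 14.0% |
| 30% | 28.5% | 27.0% | 24.0% | 21.0% |

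Section 9.5 gives the only cohort count: "As of August 2024, the dataset included 133 patients with a claim for elranatamab". At n = 133 and p = 20%, the Wilson 95% interval is 14.1% to 27.6% without loss and 9.1% to 20.9% at m = 30%. At p = 10%, 133 × 0.10 = 13.3 patients; m = 20% leaves 13.3 × 0.8 = 10.6 and m = 30% leaves 13.3 × 0.7 = 9.3. That is around the limit in section 9.4, under which counts of 1 to 10 cannot be shown. The final cohort should be larger, so this is illustration only.

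**5. Incidence.** Let a be the patients with no urinary infection in the washout whose post-index infection is coded only outside N39.0 (wrongly lost). Let b be the patients with a washout-period infection coded only outside N39.0 and a post-index N39.0 claim (wrongly counted as incident). Then

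reported incident count = true count − a + b.

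The sign depends on whether a or b is larger, and the documents inform neither.

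**6. Baseline any-infection.** This is a composite of many infection types over the whole period from myeloma diagnosis to the day before index. A patient is lost only with no N39.0 claim and no other listed infection in that entire period, so the effect is slight.

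**The case against.** The strongest reply is that there is no contradiction: Table 3 names the event and Annex 2 makes it operational, and other events, such as lymphopenia and hypokalaemia, also rest on one code. It is true that Table 3 never says any urinary tract infection in so many words. But it sets no site limit, and nothing in the protocol says that unspecified-site infection was intended. Other infection rows, such as other pneumonia and sepsis, do list site- or organism-specific codes. The mismatch between label and code remains.

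A second reply is that section 9.9 already warns that events defined by diagnosis codes may not capture the occurrence of disease. That is a general caution about claims data. It does not tell the reader that this row leaves out named kinds of urinary infection.

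Other parts of the reply stand:
- How often site-specific codes are used without N39.0 is an empirical matter on which the protocol is silent, and the loss could be small.
- A urinary infection that becomes septic may still be counted in the sepsis row, though not as UTI.
- The adverse-event outcome is exploratory, and no formal comparison is planned.
- Widening the row to N12 and N30.9x is not free: N30.9x may admit non-infectious cystitis.

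A reader might infer that UTI risk will be reported 10% to 30% too low, that every UTI estimate is biased downward, or that severe urinary infection drops out of the safety results. The documents support none of these. There is no figure for the loss, the washout can push incidence upward, and one N39.0 claim in the window keeps the patient in the count.

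**Conclusion.** The point holds as a minor mismatch between an outcome and its code list. Patients whose only coded urinary infection in the window is acute pyelonephritis or acute cystitis are not counted. The direct effect on UTI prevalence can only be downward; its size cannot be estimated from the protocol and may be modest. The effect on incidence can go either way, and the effect on baseline any-infection is slight.

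The conclusion rests on the standard meanings of N39.0, N10 and N30.0x, and on Annex 2 being applied as written, as section 9.8 says it will be. Section 9.7 allows the SAP, which is not at hand, to modify protocol plans; if it widens this row, the two documents should be brought into line.

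**What to change.** Add N10 and N30.0x to the urinary tract infection row of Annex 2 and apply the widened row everywhere it is used: the adverse-event outcome, the 60-day washout and baseline any-infection. Both codes denote infection, so they match the stated outcome. Keep N12 and N30.9x for a sensitivity analysis at most, after a check of their descriptors, because there the gain in capture may cost specificity.

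If the row is to stay as it is, rename the outcome urinary tract infection of unspecified site and add a sentence to section 9.9 stating that site-coded infections are not captured.

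Either change is a one-row or one-line edit to a retrospective query. Version 2.0 already corrected Annex 2 codes by amendment (J9415 to J9145). If interim results have used N39.0 alone, the report should note the change of definition so that interim and final UTI figures are not read as one series.
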